13.1 Sample Size Determination

The primary efficacy criterion in this study is defined as the percentage of subjects who achieve and maintain reduction of SUA < 6 mg/dL for at least 80% of the time during Treatment Period 3 and Treatment Period 6.

The percentage of responders according to the above criterion is assumed to be 65% in the SEL-212 arm and 44% in the KRYSTEXXA arm.

Using the Chi-square test for comparison between the SEL-212 arm and the KRYSTEXXA arm, and considering a one-sided alpha=5% and the statistical power of 80%, results in 69 subjects per treatment group. Taking into account that some subjects may be excluded from the modified Intent-to-Treat (mITT) analyses (Section 13.2.4), 75 subjects per treatment group will be randomized. For the sample size estimation, Chi-square test, instead of the Cochran-Mantel-Haenszel test, is used although the randomization will be stratified for tophus presence (yes/no) as there is no valid assumption of the distribution of this stratification variable within the eligible subject population.

Sample size calculations were performed with the software package nQuery Advisor® Sample Size Calculator V. 8.2.1.0.

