13.4.2 Secondary Efficacy Endpoints and Analyses

The secondary endpoints of this study are:

- Comparison in the percentage of patients on SEL-212 vs. KRYSTEXXA who achieve and maintain reduction of SUA < 6 mg/dL for at least 80% of the time during Treatment Period 6
- Comparison in the percentage of patients on SEL-212 vs. KRYSTEXXA who achieve and maintain reduction of SUA < 6 mg/dL for 100% of the time during Treatment Period 6
- Comparison in the percentage of patients on SEL-212 vs. KRYSTEXXA who achieve and maintain reduction of SUA < 6 mg/dL for at least 80% of the time during Treatment Period 3
- Comparison in the percentage of patients on SEL-212 vs. KRYSTEXXA who achieve and maintain reduction of SUA < 6 mg/dL for 100% of the time during Treatment Period 3
- Comparison between patients on SEL-212 vs. KRYSTEXXA in pre-dose SUA values > 6 mg/dL during Treatment Periods 2-6. The pre-dose SUA is collected on the dosing day prior to the dosing administration or it is collected at the visit where dosing would have occurred had the patient not been previously withdrawn from study drug.
- Comparison between patients on SEL-212 vs. KRYSTEXXA of the change in health questionnaires
- Comparison between patients on SEL-212 vs. KRYSTEXXA of gout flare incidence per 3-month period (Treatment Periods 1-3 and Treatment Periods 4-6)
- Comparison between patients on SEL-212 vs. KRYSTEXXA of gout flare frequency per 3-month period (Treatment Periods 1-3 and Treatment Periods 4-6)
- Comparison between patients on SEL-212 vs. KRYSTEXXA of the change from Baseline to Treatment Period 6 in number of tender joints
- Comparison between patients on SEL-212 vs. KRYSTEXXA of the change from Baseline to Treatment Period 6 in number of swollen joints

All statistical tests in secondary endpoints for the comparison between SEL-212 and KRYSTEXXA will be performed using one-sided tests at a type 1 error rate level of $\alpha=5\%$. In addition, 90% confidence intervals for treatment differences between SEL-212 and

KRYSTEXXA treatment groups will be computed. The efficacy analyses will be carried out based on the ITT and PP Sets. mITT analyses will be performed if appropriate.

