Comparison with regards to change of tender joints from baseline will be performed using an ANCOVA with the change from baseline value as dependent variable, treatment group and randomization stratum as independent fixed factors and the baseline number of tender joints as independent covariate. In case of non-normality the non-parametric Wilcoxon test will be used for the comparison between the treatment groups. Summary tables of the number of tender joints

for each assessment timepoint and for the change from baseline will be provided by treatment group.

Comparison with regards to change of swollen joints from baseline will be performed using an ANCOVA with the change from baseline value as dependent variable, treatment group and randomization stratum as independent fixed factors and the baseline number of swollen joints as independent covariate. In case of non-normality, the non-parametric Wilcoxon test will be used for the comparison between the treatment groups. Summary tables of the number of swollen joints for each assessment timepoint and for the change from baseline will be provided by treatment group.

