6.1. Patient Disposition and Withdrawals

Patient disposition data will be listed. Summary tables reflecting the number of patients for the following will be presented:

- Screened (or Enrolled) patients
- ITT, SS, mITT, and PP patients
- Patients who complete the study treatment
- Patients who early terminate the study treatment and reasons for early termination
- Patients who early terminate the study and reasons for early termination

Screen Failure patients will be listed.

Kaplan-Meier (KM) figures of the time to early termination of the study by treatment group and by presence of tophus will be provided.

Kaplan-Meier (KM) figures of the time to early termination of the study due to adverse event by treatment group and by presence of tophus will be provided.

Kaplan-Meier (KM) figures of the time to early study treatment discontinuation by treatment group and by presence of tophus will be provided.

Kaplan-Meier (KM) figures of the time to early study treatment discontinuation due to stopping rules by treatment group and by presence of tophus will be provided.

Kaplan-Meier (KM) figures of the time to early study treatment discontinuation due to stopping rules or due to Infusion-related reactions including infusion reaction, allergic reaction to pre-med or one of drug components and anaphylaxis, by treatment group and by presence of tophus will be provided.

In addition, stratified Log-rank test will be used to test treatment difference with presence of tophus as stratification factor for those time to event endpoint mentioned above. Unstratified Log-rank test will be used to test treatment difference for patients with presence of tophus and for patients with absence of tophus.

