7.2.5. Gout Flares Incidence and Frequency

The number and percentage of patients reporting gout flares per 3-months period and overall, i.e. Treatment Periods 1-3, Treatment Periods 4-6 and Periods 1-6, will be summarized by treatment group and will be tested using a CMH-test considering the randomization stratum. The same analysis will also be performed by patient's maximum severity of gout flare experienced within each 3-months period.

The frequency of gout flares will be summarized per 3-months period and overall and by severity for each treatment group and will be compared using ANOVA model with presence of tophus and treatment group as fixed factors. In addition for periods 4-6 and 1-6, poisson regression model will be used with number of gout flares as independent variable, treatment and presence of tophus as fixed factor, and length of follow-up for each corresponding treatment period as covariate.

7.2.6. Change from Baseline to Treatment Period 6 in Number of Tender and Swollen Joints

Comparison with regards to change in number of tender joints from baseline to end of treatment period 3 (day 0 period 4) and period 6 will be performed using an ANCOVA with the change from baseline value as dependent variable, treatment group and randomization stratum as independent fixed factors and the baseline number of tender joints as independent covariate. In case of non-normality the non-parametric Wilcoxon test will be used for the comparison between the treatment groups. Summary tables of the number of tender joints for each assessment time point and for the change from baseline will be provided by treatment group.

Comparison with regards to change of swollen joints from baseline to end of treatment period 3 (day 0 period 4) and 6 will be performed using an ANCOVA with the change from baseline value as dependent variable, treatment group and randomization stratum as independent fixed factors and the baseline number of swollen joints as independent covariate. In case of non-normality, the non-parametric Wilcoxon test will be used for the comparison between the treatment groups. Summary tables of the number of

This document is confidential.

swollen joints for each assessment time point and for the change from baseline will be provided by treatment group.

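### Change in joint counts: an undefined non-normality trigger replaces the adjusted ANCOVA with a Wilcoxon test that names neither baseline nor tophus stratum, at a power cost that depends on assumptions

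*SAP*

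**What the plan says.** SAP 7.2.6 compares the change from baseline in tender joints, and separately in swollen joints, at the end of Treatment Periods 3 and 6. The model for tender joints is an ANCOVA on change with "treatment group and randomization stratum as independent fixed factors and the baseline number of tender joints as independent covariate". Swollen joints are handled the same way with their own baseline count. For each count the fallback follows at once: "In case of non-normality the non-parametric Wilcoxon test will be used for the comparison between the treatment groups". Protocol 13.4.2 carries the same rule ("In case of non-normality the non-parametric Wilcoxon test will be used for the" comparison of the arms), and so does the Protocol Synopsis.

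Neither document says how non-normality is judged. There is no test, no threshold, and no statement of whether raw changes or model residuals are examined. Neither attaches a stratum or covariate to the Wilcoxon test. Elsewhere the SAP names stratification when it wants it: SAP 6.1 says a "stratified Log-rank test will be used to test treatment difference with presence of tophus as stratification factor", and SAP 7.1 and 7.2.1 tie the CMH tests to the tophus stratum.

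Protocol 13.4.2 has all secondary comparisons "performed using one-sided tests at a type 1 error rate level" of 5%. SAP 7.2 sets no hierarchy among the secondary endpoints.

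**The concern.** Two things are wrong with the rule. First, the choice of test depends on the data through a criterion that is not written down. The study is open-label, and SAP 2.2 treats unblinding of the analysis team as not applicable, so a fixed rule would be worth having. Second, the fallback is the weaker analysis on most plausible data. It gives up the regression on baseline that the plan chose for its main model, although a rank method can keep it.

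Joint tenderness and swelling is a named secondary objective (Protocol 6.1.2, SAP 3.2). Counts of joints are non-negative integers and probably right-skewed, so a formal normality check would usually reject. The fallback may therefore be what is reported for both endpoints.

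**Working it through.** **Step 1. The plan's own figure.** The documents contain no power calculation for joint counts. The only one is for the primary responder endpoint (Protocol 13.1): rates "assumed to be 65% in the SEL-212 arm and 44% in the KRYSTEXXA arm", and "considering a one-sided alpha=5% and the statistical power of 80%, results in 69 subjects per treatment group". With the pooled variance under the null:

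n = [1.645·√(2·0.545·0.455) + 0.842·√(0.65·0.35 + 0.44·0.56)]² / 0.21² = (1.1584 + 0.5794)² / 0.0441 = 68.48, rounded up to 69.

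This reproduces the stated figure. Since "75 subjects per treatment group will be randomized", the checks below use 75 per arm and one-sided 5%.

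**Step 2. Assumptions the documents do not supply.** These are the joint-count distributions, the baseline to follow-up correlation ρ, the effect sizes, and complete data in all 75 per arm. The tophus share is set at 70%, the figure Protocol 5.4 cites for chronic refractory gout.

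**Step 3. Normal data, by formula.** Take unit variance at both visits. The variance of change is 2(1−ρ) and the ANCOVA residual variance is 1−ρ², so their ratio is (1+ρ)/2. The Wilcoxon test has efficiency 0.955 relative to the t-test on normal data. The efficiency of Wilcoxon on change relative to ANCOVA is then 0.955(1+ρ)/2. The effect is set so that ANCOVA has 80% power: d = 2.487·√(2/75)·√(1−ρ²). At ρ = 0.5, d = 0.352 and the SD of change is 1. With effective n of 75 × 0.955 = 71.6, power is Φ(0.352/√(2/71.6) − 1.645) = 68%.

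| ρ | Relative efficiency | Wilcoxon power (ANCOVA = 80%) |
|---|---|---|
| 0.3 | 0.62 | 62% |
| 0.5 | 0.72 | 68% |
| 0.7 | 0.81 | 72% |
| 0.9 | 0.91 | 77% |

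**Step 4. Simulation, 2,000 trials per case (Monte Carlo error about 1 point).** Four tests of change are compared: the planned ANCOVA, plain Wilcoxon, stratified Wilcoxon (van Elteren), and rank ANCOVA (ranked change on treatment, tophus and ranked baseline). Shift effects are set as in Step 3. Counts are over-dispersed Poisson with baseline mean 8 or 10, and 1.5 times that with tophus. For counts, the first column gives the treated-to-control ratio of follow-up means and ρ is the simulated correlation.

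| Data | ρ | ANCOVA | Wilcoxon | van Elteren | Rank ANCOVA | Wilcoxon minus rank ANCOVA |
|---|---|---|---|---|---|---|
| Normal | 0.3 | 78.2 | 61.0 | 60.6 | 75.4 | −14.4 |
| Normal | 0.5 | 79.3 | 69.8 | 69.0 | 76.9 | −7.1 |
| Normal | 0.7 | 79.2 | 71.6 | 71.4 | 77.3 | −5.7 |
| t, 3 df | 0.3 | 81.2 | 80.8 | 80.2 | 90.8 | −10.0 |
| t, 3 df | 0.5 | 81.2 | 85.6 | 85.0 | 92.4 | −6.8 |
| t, 3 df | 0.7 | 82.4 | 91.0 | 90.2 | 94.0 | −3.0 |
| Exponential | 0.3 | 80.3 | 77.6 | 77.6 | 90.9 | −13.3 |
| Exponential | 0.5 | 78.4 | 83.4 | 83.1 | 91.4 | −8.0 |
| Exponential | 0.7 | 80.0 | 90.0 | 89.7 | 93.4 | −3.4 |
| Counts, 0.6 | 0.67 | 86.6 | 65.4 | 65.2 | 90.0 | −24.6 |
| Counts, 0.6 | 0.79 | 98.8 | 73.6 | 72.8 | 98.4 | −24.8 |
| Counts, 0.5 | 0.59 | 81.6 | 54.1 | 54.2 | 88.4 | −34.3 |
| Counts, 0.6 | 0.58 | 93.0 | 72.6 | 72.2 | 93.4 | −20.8 |
| Counts, 0.7 | 0.80 | 88.2 | 75.9 | 75.4 | 89.8 | −13.9 |
| Counts, 0.4 | 0.56 | 96.8 | 58.0 | 57.5 | 99.0 | −41.0 |

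Adding the stratum to the Wilcoxon test moves power by less than 1 point throughout. Only the count cases give tophus any effect on the outcome. Nearly all the gap therefore comes from the baseline regression.

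**Step 5. Would the fallback be reached?** The plan names no check, so Shapiro-Wilk at 5% serves as a stand-in. In 12 further count scenarios (baseline mean 8 to 12, ρ 0.3 to 0.7, 30% reduction, 1,500 trials each) it rejected in 97 to 100% of trials on ANCOVA residuals and 85 to 100% on raw change. In those scenarios Wilcoxon had 32 to 79% power, rank ANCOVA 63 to 98% and the planned ANCOVA 57 to 99%. The loss to rank ANCOVA was 19 to 33 points.

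**Step 6. Type I error.** Under the null in the six count cases of Step 4 (1,000 trials each), ANCOVA rejected in 4.7 to 5.8%, Wilcoxon in 4.5 to 5.7% and rank ANCOVA in 4.2 to 6.2%.

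**The case against.** The strongest reply has four parts.

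- **Wording.** Neither document calls the Wilcoxon test unstratified or unadjusted; it is simply under-specified. That stands. The contrast with SAP 6.1 makes the plain test the natural reading, but it remains an inference.
- **Baseline.** A reader might infer that baseline is thrown away. It is not: the endpoint is change, so baseline is still subtracted with a fixed coefficient of 1. Only the fitted adjustment is lost.
- **Choice of distribution.** Over-dispersed counts with a proportional effect are unfavourable to Wilcoxon on change. With a shift effect on heavy-tailed or exponential data it runs from about 3 points below the planned ANCOVA to 10 points above it. That stands, and no joint-count distribution comes from the documents. Rank ANCOVA still beats Wilcoxon by 3 to 13 points in those cases, so the recommendation does not hinge on the family. With small counts (baseline mean 2 to 3, 20 to 30% zeros) power is low for every method but the gap remains: about 39% against 59 to 65%.
- **Target.** Ranking the end count, or a count model giving a rate ratio, would move away from change from baseline. That is fair. Ranking the change does not, and keeping the planned ANCOVA as the main analysis avoids the issue.

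**Conclusion.** The point holds. The switch has no stated trigger and would probably be used. On the natural reading it replaces a baseline-adjusted analysis with a less efficient one. Against an adjusted rank analysis the assumed scenarios in the Step 4 table give a loss of 3 to 41 points. For over-dispersed counts it is 14 to 41, and above 20 in five of six cases. Against the planned ANCOVA the result runs from a loss of about 39 points (counts) to a gain of 10 (exponential, ρ = 0.7). The switch is not needed for validity in these scenarios, since ANCOVA held its level on skewed counts.

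Three stronger readings are not supported.

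- A large power loss cannot be stated as fact, because the documents give no SD, correlation or effect size for joint counts.
- Losing the stratum is not a material power cost here; it is worth about 1 point or less.
- A reader might infer an inflated type I error. In one null scenario ANCOVA rejected in 4.6%, Wilcoxon in 5.1%, and the two disagreed in 6.9%. Taking whichever was significant would reject in (4.6 + 5.1 + 6.9)/2 = 8.3%. The plan does not authorise that choice, and no inflation from the rule as written has been shown. The undefined trigger is a transparency weakness.

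The consequence is confined to two secondary endpoints outside any hierarchy. The primary CMH analysis is unaffected.

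**What to change.** Delete the normality-triggered sentence for both counts and pre-specify one analysis adjusted for baseline count and tophus. Either of these would do:

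- keep the planned ANCOVA on change as the main analysis, with rank ANCOVA (ranked change on treatment, tophus and ranked baseline count) as the non-parametric sensitivity analysis; or
- make rank ANCOVA the main test and report the ANCOVA mean difference with its confidence interval beside it.

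If a Wilcoxon test is kept, state what triggers it, whether the check applies to residuals or raw change, and whether the test is stratified. The cost is one paragraph in SAP 7.2.6, with the difference from Protocol 13.4.2 recorded in SAP 7.4. The baseline counts and tophus status are already collected, so no new data are needed. Make the change before joint counts are examined by arm.

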7.3. Subgroup Analyses

In the event of a prolonged gout flare which is not successfully managed, Investigators will most likely treat patients with corticosteroids which will have a downstream effect on the duration of flares, swollen/tender joint counts and QOL assessments. In order to better extrapolate the results, a subgroup analysis may be conducted for patients who receive “additional gout flare treatment”. The statistical analysis and summaries described in sections 7.2.2 through 7.2.6 may be repeated for the subgroup of patients who receive “additional gout flare treatment” as well as by primary efficacy endpoint (responder vs. non-responder).

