10.5 Premedication

10.5.1 Gout Flares (Prevention and Treatment)

All patients that meet all inclusion and exclusion criteria will be premedicated for gout flare prevention. The regimen will begin at least 7 days prior to the first dosing of study drug and continue for as long as the patient is participating in the clinical study.

Patients not already taking colchicine will receive colchicine 1.2 mg as a single loading dose followed by 0.6 mg QD for the remainder of participation in the trial. If the patient cannot tolerate the loading dose level of 1.2 mg, then the patient will initiate and maintain colchicine at 0.6 mg. Patients with a documented medical reason that describes a contraindication to colchicine will receive ibuprofen 600 mg TID or an equivalent NSAID unless the patient has a contraindication to NSAID. At the discretion of the Investigator, a proton pump inhibitor may be prescribed with the NSAID as gastric prophylaxis. Patients with documented medical reasons that describe contraindications to both colchicine and NSAIDs will receive no premedication for gout flare.

Patients who began receiving a NSAID as gout flare prevention medication due to a contraindication to colchicine should continue to receive the NSAID during study participation. These medications will be supplied by the clinic.

As gout flares are expected to occur despite preventative premedication, incidents of gout flare are to be recorded as an AE and treated at the discretion of the Investigator to provide adequate patient care.

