13.4.3 Subgroup Analyses

In the event of a prolonged gout flare which is not successfully managed, Investigators will most likely treat patients with corticosteroids which will have a downstream effect on the duration of flares, swollen/tender joint counts and QOL assessments. In order to better extrapolate the results, a subgroup analysis will be conducted for patients who receive “additional gout flare treatment” in each arm for these objectives. Details of this subgroup analysis will be provided in the SAP.

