7.4. Deviation from Analyses Planned in Protocol

7.4.1. Additional analyses

The following analyses are added even though they are not included in the protocol:

- Interim analysis.
- Subgroup analyses on the secondary endpoint by patient's primary efficacy endpoint (responder vs. non-responder).

The following analyses have been added as a result of the impact of Covid-19 on the study which may result in a larger anticipated number of subjects not completing the study and therefore not undergoing the assessments required for the primary efficacy endpoint or the study being stopped prematurely by sponsor decision. This is in line with FDA Guidance on Conduct of Clinical Trials of Medical Products during COVID-19 Pandemic Guidance for Industry, Investigators, and Institutional Review Boards.

- Additional analyses suggested to primary endpoint as sensitivity analyses to determine if the impact that these have on the conclusions of the study and to describe the impact of Covid-19 on the study performance.
- A sensitivity analysis which limited the analysis to results processed in the central laboratory to determine if this resulted in different conclusions to those found from the full analysis to determine consistency in laboratory testing between central and local laboratories.
- Kaplan-Meier analysis of withdrawal from study by treatment arm and presence of tophus to determine if subjects withdraw from the study in different proportions and at different rates within the treatment groups and depending on the presence of tophus.
- Kaplan-Meier analysis of withdrawal from study due to an adverse event by treatment arm and presence of tophus to determine if subjects experience adverse events in different proportions and at different rates within the treatment groups and depending on the presence of tophus.
- Poisson regression with number of gout flares experienced during treatment periods 1-6 as the dependent variable, treatment and the presence of tophus as independent variables and length of follow up as a covariate. The ITT population would be used to conduct this analysis. Similar analysis is done for periods 4-6.

This document is confidential.

8. Safety

The population used for safety analyses will be the Safety Set (SS). Safety will be assessed on the basis of adverse event (AE), clinical laboratory data, ECG parameters, physical examinations, and vital signs.

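### Between-arm tests repeated inside flare-treated patients and inside primary responders or non-responders condition on post-randomisation outcomes and should be descriptive only

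*SAP*

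**What the plan says.** Protocol 13.4.3 and SAP 7.3 both expect that after a prolonged flare "Investigators will most likely treat patients with corticosteroids which will have a downstream effect on the duration of flares, swollen/tender joint counts and QOL assessments". Their response is a subgroup analysis.

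- Protocol 13.4.3 commits to it: "a subgroup analysis will be conducted for patients who receive" additional gout flare treatment in each arm. It ties the analysis to flare duration, joint counts and quality of life, and adds: "Details of this subgroup analysis will be provided in the SAP".
- SAP 7.3 makes it optional: "In order to better extrapolate the results, a subgroup analysis may be conducted for patients who receive" such treatment. It then sets the scope: "The statistical analysis and summaries described in sections 7.2.2 through 7.2.6 may be repeated for the subgroup of patients who receive" that treatment, and also by primary response. Sections 7.2.2 to 7.2.6 cover HAQ-DI, PrGA, SF-36, flare incidence and frequency, and tender and swollen joints.
- SAP 7.4.1 lists the second split among analyses added to the protocol, without any *may*: "Subgroup analyses on the secondary endpoint by patient's primary efficacy endpoint (responder vs. non-responder").

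Neither document defines additional gout flare treatment. Protocol 10.5.1 leaves the decision to the site: "incidents of gout flare are to be recorded as an AE and treated at the discretion of the Investigator". The ITT and PP analyses of the same endpoints stay in place (Protocol 13.4.2).

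**The concern.** Randomisation balances the arms as a whole. It does not balance the patients who later flare and are treated, or those who later reach the urate target. If one drug prevents more flares, those who still need flare treatment on that drug tend to have more severe disease than their counterparts in the other arm. A test inside the subgroup then compares unlike patients and can make the better drug look worse on joints and quality of life. The responder split has the same problem, because the plan itself assumes that response differs by arm. In an open-label trial, discretionary flare treatment adds a further route for the subgroups to differ, in a direction that cannot be predicted.

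The subgroup also does not answer the question that prompts it. Restricting to treated patients leaves the steroid effect in every observation. At stake is an exploratory p-value that readers could take as a treatment effect in a population of clinical interest.

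**Working it through.** **The plan's own figure.** The 65% and 44% response rates come from Protocol 13.1 and SAP 3.5. The pooled-variance formula with one-sided 5% and 80% power gives n = [1.645 × √(2 × 0.545 × 0.455) + 0.842 × √(0.65 × 0.35 + 0.44 × 0.56)]² / 0.21² = 68.5, so 69 per arm, as stated; 75 per arm are randomised. The documents give no flare-treatment rate, joint-count SD or link between severity and flares. Those inputs are assumed below.

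**1. Flare incidence over Treatment Periods 1-6 in the flare-treated subgroup.** Suppose treatment is given only for an on-study flare. Then every member has a flare. In each tophus stratum, with n1 and n2 patients, N = n1 + n2, m flares in total and a flares in arm 1, we have m = N and a = n1.
- CMH numerator term: a − n1·m/N = n1 − n1 = 0.
- CMH variance term: n1·n2·m·(N − m) / [N²(N − 1)] = 0.

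The statistic is 0/0, so the test is undefined.

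**2. Flare incidence per 3-month period.** These tests still run. Assume patient flare rates vary as a gamma variable with shape 1 and mean 1. Let the mean flares be 1.2 then 0.4 on SEL-212 and 1.5 then 1.0 on KRYSTEXXA (Periods 1-3, then 4-6), with each flare treated with probability 0.3. For a total mean λ, P(no event) = 1/(1 + λ).
- All patients, Periods 1-3: 1 − 1/2.2 = 54.5% vs 1 − 1/2.5 = 60.0%.
- Flare-treated, SEL-212: P(treated) = 0.48/1.48 = 0.3243; P(treated, no flare in 1-3) = 1/2.2 − 1/2.32 = 0.0235; incidence 1 − 0.0235/0.3243 = 92.7%.
- Flare-treated, KRYSTEXXA: P(treated) = 0.75/1.75 = 0.4286; 1/2.5 − 1/2.8 = 0.0429; incidence 90.0%.

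The direction reverses. Over the scenarios with a treatment difference in flares and treatment probabilities of 0.3 to 0.6, subgroup incidence is 87-93% in Periods 1-3 and 37-85% in Periods 4-6: distorted, but not empty.

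**3. Joint counts in the flare-treated subgroup, no true effect.** Assume severity U ~ N(0,1), baseline count 6 + 3U + N(0, SD 3), Period 6 count 4 + 3U + N(0, SD 3), and P(treated flare) = expit(bU − d) on SEL-212 and expit(bU) on KRYSTEXXA. Fit an ANCOVA of change on arm and baseline; positive values are against SEL-212.

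| b, d | Treated flare, KRYSTEXXA vs SEL-212 | Subgroup difference (joints) | Full sample | Subgroup size at 75 per arm | SE at that size |
|---|---|---|---|---|---|
| 1, 0 | 50% vs 50% | 0.00 | 0.00 | about 38 vs 38 | about 0.85 |
| 1, 1 | 50% vs 30% | +0.29 | 0.00 | about 38 vs 23 | 0.98 |
| 1.5, 1.5 | 50% vs 25% | +0.51 | 0.00 | about 37 vs 19 | 1.03 |

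Relative to the standard error the bias is 0.29/0.98 = 0.3 and 0.51/1.03 = 0.5. With a milder flare difference (d = 0.3, b = 1) it is about +0.09.

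**4. Responder split at the plan's 65% vs 44%.** Let response occur when a standard normal prognosis exceeds an arm-specific cut, and let the outcome correlate ρ with prognosis, with no treatment effect. Mean prognosis is φ/p in responders and −φ/(1 − p) in non-responders, where φ is the normal density at the cut.
- p = 0.65: φ = 0.3704, giving 0.570 and −1.058.
- p = 0.44: φ = 0.3944, giving 0.896 and −0.704.
- SEL-212 minus KRYSTEXXA: −0.327 in responders and −0.354 in non-responders, multiplied by ρ.

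For assumed ρ of 0.3 to 0.7, SEL-212 looks worse by 0.10 to 0.23 SD among responders and 0.11 to 0.25 SD among non-responders. Expected sizes are 75 × 0.65 = 49 vs 75 × 0.44 = 33 responders and 26 vs 42 non-responders.

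**The case against.** The case for leaving the text alone has real weight. The repeats are optional in SAP 7.3, the stated aim is only to help extrapolate the results, no alpha is attached to them, and the ITT and PP comparisons remain. The bias sizes rest on assumed inputs and are small against the standard error at this sample size. The secondary tests are one-sided in favour of SEL-212. In the model of step 3 the bias runs against SEL-212, so false rejection in its favour falls to between 1% and 3%, below the nominal 5%. All of this stands, and it limits the point to exploratory output.

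It does not remove the point. The protocol still says the analysis *will* be done, SAP 7.4.1 lists the responder split as added, and the subgroup term is undefined although the protocol defers its detail to the SAP. Membership could therefore be settled after the data are seen. In step 4, both halves of the responder split lean the same wrong way, which could be mistaken for corroboration.

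A reader might also infer that the flare-incidence test as a whole is empty. The documents do not support that. SAP 7.2.5 tests three windows, and the listed secondary endpoint is per 3-month period; only the Periods 1-6 repeat among flare-treated patients loses its content, and only if treatment follows an on-study flare. The flare-frequency models and the responder repeats are not empty either.

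**Conclusion.** The point holds as one about exploratory subgroup comparisons. Both groups are defined by post-randomisation events that treatment can change, so between-arm tests inside them are not protected by randomisation. That conclusion needs no simulation.

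The size does. It is about 0.3 to 0.5 joints in the flare-treated subgroup and 0.10 to 0.25 SD in the responder split. Only the 65% and 44% rates come from the plan; severity links, SDs and flare rates are assumed. The flare-treated bias disappears if treatment does not change flares and, in the models used here, grows as the drug works better.

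It would be wrong to conclude that the plan's randomised comparison of joints, quality of life or flares is broken, or that a false superiority claim for SEL-212 is likely. The ITT analyses are kept, and the modelled bias runs against the arm with fewer flares or more responders.

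**What to change.** In SAP 7.3 (with the matching entry in 7.4.1) and Protocol 13.4.3:

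1. Present both subgroups as descriptive summaries by arm, without between-arm p-values or treatment-effect claims.
2. Omit flare incidence over Treatment Periods 1-6 in the flare-treated subgroup.
3. Define additional gout flare treatment for analysis purposes before database lock.
4. Reconcile the protocol's *will* with the SAP's *may*.
5. State that conclusions on joints and quality of life rest on the full ITT comparison.

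The cost is a few lines of text and the loss of some exploratory p-values. No data collection changes.

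A supplementary ITT analysis of flare steroids is optional. It would need a named imputation method and a justified time window. Joints and questionnaires have only two scheduled post-baseline visits (Period 4 Day 0 and Period 6 Day 28), so little is left to impute from. It would also have to account for the steroid premedication before every infusion (Protocol 10.5.2), which differs by arm: up to 6 vs 12 infusions, the last scheduled on Day 140 vs Day 154. The Day 168 assessment therefore falls 168 − 140 = 28 days after the last scheduled SEL-212 infusion but 168 − 154 = 14 days after the last KRYSTEXXA infusion.
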